3.1.1.2. Treatment Period and Follow-up Period

The Treatment Period for each participant starts with Day 1 and is scheduled to end 28 days after each dose of vaccine. In Part A, for unvaccinated SOT and healthy participants who receive the 2-dose regimen (Group A1 and Group A5), the Follow-up Period starts with Day 58 and is scheduled to end on Day 394 (12 months after the second dose). The Follow-up Period for unvaccinated SOT participants who receive the 3-dose regimen (Group A2) starts with Day 114 and is scheduled to end on Day 450 (12 months after the third dose). The Follow-up Period for previously vaccinated participants (Group A3) starts with Day 29 and is scheduled to end on Day 365 (12 months after dose 3). In Part B (Group B2, Group B3, Group B4, and Group B5), Follow-up Period starts with Day 29 and is scheduled to end on BD-D181 (6 months after BD).

For Part A (Group A1, Group A2, Group A3, and Group A5): On Day 1, after the completion of the scheduled assessments ([Section 10.1](#)), all participants will be administered a single IM dose of 100 μ g of mRNA-1273 ([Section 5.3.2](#)). Participants will be closely monitored for safety and will remain at the study site for observation for at least 30 minutes after dosing. For unvaccinated SOT and healthy participants (Group A1, Group A2, and Group A5), the second dose of vaccine will be administered on Day 29. Unvaccinated SOT recipients who consent to receive a third dose of

vaccine (Group A2) will receive it on Day 85. Previously vaccinated SOT recipients (Group A3) will receive dose 3 on Day 1. Participants will be monitored for 12 months after the second and third dose (as applicable) of vaccine for safety, immunogenicity, and breakthrough SARS-CoV-2 infection or COVID-19.

For Part B (Group B2, Group B3, Group B4, and Group B5): On BD-D1, after the completion of the scheduled assessments, at least 4 months after the last dose, all participants will be administered a single intramuscular (IM) dose of 100 µg BD of mRNA-1273. Participants will be closely monitored for safety and will remain at the study site for observation for at least 30 minutes after dosing. Participants will be monitored for 6 months after the BD for safety, immunogenicity, and breakthrough SARS-CoV-2 infection or COVID-19.

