4.2. Study Eligibility Criteria (Part B)

4.2.1. Inclusion Criteria (Group B2, Group B3, Group B4, and Group B5)

1. a. Participants must have been previously enrolled in the mRNA-1273-P304 study, are actively participating in Part A and are at least 4 months from the last dose, or
b. Is an adult male or female individual, at least 18 years of age at the time of signing informed consent, is EITHER a kidney or a liver (single organ) transplant recipient who

is at least 90 days after transplantation at the time of consent AND who completed primary vaccination series (3 doses for mRNA COVID-19 vaccine; 2 doses for non-mRNA COVID-19 vaccine or at least 1 dose of non-mRNA combined with 1 dose of mRNA COVID-19 vaccine) under the EUA who are at least 4 months from the last dose. All primary COVID-19 vaccination series must be completed after transplant.

2. Female participants of childbearing potential may be enrolled in the study if the participant has a negative pregnancy test on the day of the booster dose injection (BD-Day 1).

4.2.2. Exclusion Criteria (for Participants who Completed Primary Vaccine Series under EUA) (Group B4)

Exclusion Criteria in Part A will apply except prior or planned administration of a coronavirus vaccine and current treatment with investigational agents for either prophylaxis against COVID 19.

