5.4. Study Treatment Compliance

All doses of vaccine will be administered at the study site under direct observation of medically qualified study staff and appropriately recorded (date and time) in the eCRF. Qualified study site staff will confirm that the participant has received the entire dose of vaccine. If a participant does not receive vaccine or does not receive all of the planned doses, the reason for the missed dose will be recorded. Data will be reconciled with study site accountability records to assess compliance.

Participants who miss the second or third dose due to noncompliance with the visit schedule and not due to a safety pause will still be required to follow the original visit and testing schedule as described in the protocol and their regimen schedule. Unless consent is withdrawn, a participant who withdraws or is withheld from receiving the second or third dose will remain in the study and complete all safety and immunogenicity assessments required through the participant's last scheduled study visit.

The study site staff are responsible for ensuring that participants comply with the allowed study visit windows. If a participant misses a visit, every effort should be made to contact the participant and complete a visit within the defined visit window ([Section 10.1](#)). If a participant does not complete a visit within the time window, that visit will be classified as a protocol deviation. The participant will continue with subsequent scheduled study visits. All safety requirements of the missed visit will be captured and included in the subsequent visit.

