6. DELAYING OR DISCONTINUING STUDY TREATMENT AND PARTICIPANT WITHDRAWAL FROM THE STUDY

6.1. Criteria for Delay of Vaccine Administration

6.1.1. Individual Participant Criteria for Delay of Study Vaccination

Body temperature (oral) must be measured on dosing visits before vaccine administration. The following events constitute criteria for delay of injection, and if either of these events occur at the time scheduled for dosing, the participant may receive the study injection at a later date within the time window specified in the applicable SoE ([Section 10.1](#)), or the participant may be discontinued from dosing at the discretion of the investigator ([Section 6.2](#)):

- Acute moderate or severe infection with or without fever at the time of dosing
- Fever, defined as body temperature $\geq 38.0^{\circ}\text{C}/\geq 100.4^{\circ}\text{F}$ at the time of dosing (oral temperature preferred)

Participants with a minor illness without fever, as assessed by the investigator, can be vaccinated. Participants with a fever of $\geq 38.0^{\circ}\text{C}/\geq 100.4^{\circ}\text{F}$ will be contacted within the time window acceptable for participation and re-evaluated for eligibility. If the investigator determines that the participant's health on the day of dosing temporarily precludes injection, the visit should be rescheduled within the allowed interval for that visit if possible or at a time the participant is clinically stable according to the judgement of the investigator.

If a participant takes a prohibited drug therapy, an injection could be delayed within the visit window based on the joint decision of the investigator and the CRO's medical monitor ([Section 5.5.3](#)).

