17. Trained study site personnel will call all participants to collect information relating to any AEs, MAAEs, SAEs, AESIs, AEs leading to discontinuation from dosing and/or study participation withdrawal, information on concomitant medications associated with those events, and any nonstudy vaccinations. In addition, study personnel will collect information on known participant close contact exposure to someone with known COVID-19 or SARS-CoV-2 infection and on participant experience of COVID-19 symptoms.
18. All concomitant medications and nonstudy vaccinations will be recorded through 28 days after injection; all concomitant medications relevant to or for the treatment of an SAE, confirmed (biopsy-proven) or suspected events of organ transplant rejection, or MAAE will be recorded from Day 1 through the final visit (Day 365). In addition, the 2 previous doses of the Moderna COVID-19 vaccine will be recorded in the participant's eCRF regardless of the timing.
19. All immunosuppressant medications, for 3 months prior to Screening and throughout the study. Any change in the maintenance therapy should be recorded and the reason for the change documented.

Table 10: Booster Dose Phase (Part B: Group B2, Group B3, Group B4, and Group B5)

Visit Number	BD-1	BD-1a	BD-2	-	BD-3	-	BD-4
Type of Visit	C	C	C	SC	C	SC	C
Study Visit Day	BD-D1 ¹ (D205 for SOTr who received 3 doses; D120 for SOTr who received 1 dose; D149 for healthy cohort; at least 4 mos from last dose for SOTr who received primary series under EUA)	BD-D4	BD-D8	14 and 21 days after BD-D1 (BD-D15, BD-D22)	BD-D29	BD-D59, BD-D89, BD-D119, BD-149	BD-D181
Window Allowance (Days)	- 14 days	-2	+3	+3	-3/+14	+3	-3/+14
Days Since Most Recent Vaccination (in Part B)	0	3	7	-	28	-	180
Informed consent form, demographics, concomitant medications, medical history	X						
Review of inclusion and exclusion criteria	X						
Physical examination including height and weight ²	X				X		X
Lymph node assessment ³	X		X				
Vital signs ⁴	X		X		X		X
Pregnancy testing ⁵	X						
Immunogenicity Assessment							
Blood for immunologic analysis and assessment of Ab against nonvaccine antigen ⁶	X				X		X

Visit Number	BD-1	BD-1a	BD-2	-	BD-3	-	BD-4
Type of Visit	C	C	C	SC	C	SC	C

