Recording of suspected AND confirmed organ transplant rejection ¹⁷	X	X	X	X	X	X	X
Recording of concomitant medications and nonstudy vaccinations ¹⁷	X	X	X	X	X	X	X
Recording of concomitant immunosuppressant medications ¹⁸	X	X	X	X	X	X	X

Abbreviations: AE = adverse event; AESI = adverse event of special interest; AR = adverse reaction; BD = booster dose; C = clinic visit; D = day; eDiary = electronic diary; ICF = informed consent form; MAAE = medically attended AE; NP = nasopharyngeal; SAE = serious adverse event; SC = safety (phone) call; SOTr = solid organ transplant recipients.

Note: In accordance with FDA Guidance on Conduct of Clinical Trials of Medical Products during COVID-19 Public Health Emergency (DHHS 2020), investigators may convert study site visits to home visits or telemedicine visits with the approval of the Sponsor.

1. A BD may be administered to all eligible participants who are currently enrolled in Part A or Part B provided there are no current contraindications for further dosing ([Section Error! Reference source not found.](#)). A participant who is currently in the Convalescent Period may come in for a BD-1 visit and receive a BD as long they are no longer symptomatic, and this includes the possibility for a Convalescent Visit Day 28 to overlap and be combined with a BD-1 visit. For eligible participants in Part A who are at least 4 months from completion of primary vaccination series who consent to receive BD, the study visit or follow-up 4 months after their last dose in Part A may overlap with BD-D1. In this case, a participant will need to come in for the BD-D1 visit at least 4 months after the last dose and then follow Part B.

2. Symptom-directed physical examination will be performed at the BD-Day 1. At visits BD-2 (BD-D29), and BD-3 (BD-D181), a symptom-directed physical examination may be performed at the discretion of the investigator. Any clinically significant finding identified during a study visit should be reported as a MAAE.
3. On dosing day before injection, the arm receiving the injection should be examined and the associated lymph nodes should be evaluated.

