4. Vital signs are to be collected pre- and post-dosing (participant will be seated for at least 5 minutes before all measurements are taken per [Section 7.1.4](#)) on the day of injection (BD-D1). Participants who are febrile (body temperature $\geq 38.0^{\circ}\text{C}/100.4^{\circ}\text{F}$) before dosing (BD-D1) must be rescheduled to receive the injection. Afebrile participants with minor illnesses can be vaccinated at the discretion of the investigator.
5. The pregnancy test at the BD-1 visit will be a point-of-care urine test. At the discretion of the investigator, a pregnancy test either via blood or point-of-care urine test can be performed.
6. Samples for immunogenicity (bAb against SARS-CoV-2 spike protein and neutralizing antibody against SARS-CoV-2) and assessment of SARS-CoV-2 bAb against the nonvaccine antigen (nucleocapsid protein) must be collected prior to dosing on BD-D1.
7. For assessment of cellular immune response, blood samples will be collected on Day 1 (prior to dosing), and Day 8 from previously vaccinated SOT recipients (kidney or liver).
8. All participants who chose to receive a BD. Serum sample from two ~ 4 mL blood draws. Biomarker plasma and biomarker serum samples will be stored for potential future biomarker assessment.
9. Samples for safety laboratory assessments (serum creatinine, urine protein, and UPCR for kidney transplant recipients only; ALT, AST, ALP, and bilirubin for liver transplant recipients only) must be collected prior to dosing on BD-D1.
10. After BD-D29, the investigator will review standard-of-care kidney and liver laboratory assessments and report any laboratory-related AEs and suspected or confirmed events of organ transplant rejection until the EOS.
11. Post-dosing, participants will have a 30-minute observation period.

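### Table 10's booster window runs only backwards from the target day, so almost every booster that meets the four-month rule is out of window on paper

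*Protocol*

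**What the plan says.** Protocol Appendix 1, Table 10, gives the BD-D1 study days as "D205 for SOTr who received 3 doses; D120 for SOTr who received 1 dose; D149 for healthy cohort". Group B4 has no fixed day, only the four-month minimum. The window allowance for BD-D1 is minus 14 days, printed the same way in every header of the table. Other Part B visits have a plus side, for example -3/+14 at BD-D29.

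Three places set a minimum interval and no maximum:

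- Section 4.2.1, criterion 1a, admits Part A participants who "are actively participating in Part A and are at least 4 months from the last dose".
- Section 3.1.1.2 says that "at least 4 months after the last dose, all participants will be administered" the booster.
- Table 10, footnote 1, says "a participant will need to come in for the BD-D1 visit at least 4 months after the last dose and then follow Part B".

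On visits outside the window, Section 5.4 states: "If a participant does not complete a visit within the time window, that visit will be classified as a protocol deviation".

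SAP Section 5.3.2 (Per-Protocol Set, Part B) requires that the planned booster was received per schedule. SAP Section 5.3.3 (Per-Protocol Immunogenicity Set, Part B, the primary immunogenicity population) requires the same of Part A roll-overs. Neither section says what that means in days.

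The Synopsis (Study Periods and Study Duration) and Section 3.1.1 give Day 129 for the healthy participants' booster.

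**The concern.** The target days sit at about the four-month mark, so an allowance that only looks backwards covers days on which the participant is not yet eligible. The days on which the participant is eligible have almost no allowance.

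Other text plainly expects boosters after the target. Footnote 4 of Table 10 says participants who are febrile "before dosing (BD-D1) must be rescheduled to receive the injection". Section 6.1.1 says that after a delay "the participant may receive the study injection at a later date within the time window specified in the applicable SoE", yet for BD-D1 that window contains no date after the target. Group A2 follow-up "starts with Day 114 and is scheduled to end on Day 450 (12 months after the third dose"), so a participant can be active and eligible long after D205.

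At stake is who belongs to the primary Part B immunogenicity set. If the SAP's on-schedule condition were applied with Table 10's window, eligible B2 and B3 participants boosted after the target would drop out of the BD-D29 neutralizing-antibody endpoint for Moderna-primary-series recipients. The study is open-label, so it is better to fix the rule in advance than to settle it once data are in view.

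**Working it through.** **Inputs.** Nominal last Part A dose: B2 Day 85, B3 Day 1, B5 Day 29. Targets: 205, 120 and 149 (Table 10). Window: target minus 14 to target. The documents do not convert 4 months to days. I assume M = 120, with 112 (16 weeks) and 123 (the longest four calendar months) as the range.

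**Where the targets come from.** Target minus last dose:

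- B2: 205 - 85 = 120 days
- B5: 149 - 29 = 120 days
- B3: 120 - 1 = 119 days

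So 120 days reproduces the B2 and B5 targets exactly. The B3 target is one day short.

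**Days both eligible and in window.** First eligible day = last dose + M. Overlap = max(0, target - (last dose + M) + 1), for a nominal last dose.

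| Group | Printed window | M = 112 | M = 120 | M = 123 |
|---|---|---|---|---|
| B2 | D191 to D205 | from D197: 9 | from D205: 1 | from D208: 0 |
| B3 | D106 to D120 | from D113: 8 | from D121: 0 | from D124: 0 |
| B5 | D135 to D149 | from D141: 9 | from D149: 1 | from D152: 0 |

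**Permitted late dose 3 (B2).** The targets are fixed study days and do not move with the actual dose. Dose 3 may be given up to D92 (85 + 7), or D106 (85 + 21) under the pandemic extension.

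- From D92: D205 is only 113 days later. At M = 120 the first eligible day is 92 + 120 = D212, so the overlap is zero. At M = 112 it is D204, which leaves two days.
- From D106: D205 is 99 days later. The first eligible day is D226 at M = 120 and D218 at M = 112, so the overlap is zero either way.

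An early dose 3 at D82 helps a little: at M = 120 the first eligible day is D202, which leaves four days.

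**Are boosters after the target likely?** Amendment 4, which added Part B, is dated 20 December 2021 (SAP Section 1). A participant with Day 1 on or before 29 May 2021 was already past D205 on that date. If enrolment began in April 2021 as estimated in the Synopsis, April entrants were at D235 to D264, that is 30 to 59 days past D205, before any IRB approval. Actual enrolment dates are not given. The argument covers B2 only. Group A3 came in with Amendment 3 (23 August 2021), and a Day 1 on that date is exactly D120 on 20 December 2021.

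**Day 129.** 129 - 29 = 100 days after dose 2. That is short of 4 months by 12, 20 or 23 days at M = 112, 120 or 123, and it disagrees with D149.

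**The case against.** The strongest reply is that Table 10 should be read with its own footnote. Footnote 1, criterion 1a and Section 3.1.1.2 all describe an open-ended minimum, so sites would simply boost later, and no text ties the SAP's on-schedule condition to the window cell. SAP Section 6.2.7 leaves the major-deviation rules to be finalized before database lock, and Section 5.3.3 excludes only for major deviations that affect immune response. All of this stands against claiming an actual loss of participants. It does not repair the cell, which still states a different rule, and it leaves the SAP condition without a definition.

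The cell may be a slip for plus or minus 14 days. That would extend the B2 window to D219 (205 + 14) and ease the late side, but the early half would still conflict with the four-month minimum.

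For B3, one could count D120 as 120 days because Table 9 labels D180 as 180 days. Table 9 also labels D8 as 7 days and D29 as 28 days, so it offers no consistent convention. Subtraction, as used for B2 and B5, gives 119. The alternative count would add one day at each M below 123.

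A reader might infer three stronger points that the documents do not support:

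- **Early boosters are licensed.** They are not: criterion 1a bars them and Section 4 forbids waivers.
- **Dosing is blocked after the target.** It is not: Section 6.1.1 also allows injection once the participant is clinically stable.
- **Group B4 would be lost from the primary immunogenicity set.** It would not: Section 5.3.3 admits B4 through a separate clause without the schedule condition.

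Day 129 appears in study-duration text, and Section 7 says timing follows Section 10.1, so D149 should govern. It remains a contradiction in three places.

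**Conclusion.** The point holds as a contradiction between a stated window and the eligibility rule. At 120 days, a participant dosed on the nominal day has one in-window eligible booster day in B2, none in B3 and one in B5. Across 112 to 123 days the ranges are 9 to 0, 8 to 0 and 9 to 0. With dose 3 at D92 or D106, B2 has none at 120 days. Day 129 is a separate, plain error.

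It would be tempting to conclude that the SAP will remove late-boosted participants from the primary set. The documents do not say so: exclusion depends on how an undefined condition is applied and on deviation rules not yet written. The number of participants affected cannot be computed, because neither booster dates nor enrolment dates are given.

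Severity is minor to moderate. The effect on the primary analysis is confined to B2 and B3 membership, since B5 is outside the SOT primary endpoints. Four features limit it further: an mITT sensitivity analysis is planned (SAP Section 6.4), Part B visit windows count from the booster date (SAP Appendix B, Table 3), the interval from last dose to booster is summarized (SAP Section 6.2.6), and no hypothesis is tested.

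**What to change.** In Table 10, give BD-D1 no minus allowance and an open or explicitly stated plus side, counted from the actual last dose rather than a fixed study day.

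State 4 months once, in days, and align the targets with it. At 120 days, B2 (D205) and B5 (D149) stand and B3 becomes D121. Alternatively, keep D120 for B3 and set the minimum at 119 days.

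Change Day 129 to Day 149 in both Synopsis locations and in Section 3.1.1.

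In SAP Sections 5.3.2 and 5.3.3, define an on-schedule booster for roll-overs as one given at or after that same minimum interval from the actual last dose, and within any upper limit the table states. The SAP and Table 10 must use the same number: a 120-day SAP minimum beside an unchanged D120 target would exclude a B3 participant boosted exactly on target, at 119 days.

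The cost is a protocol clarification, or a formal amendment with IRB approval if the sponsor judges that Section 10.2.7 requires one, plus one SAP definition before database lock. No extra participants, visits or procedures are needed.

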10.2. APPENDIX 2: Study Governance Considerations

10.2.1. Regulatory and Ethical Considerations

This study will be conducted in accordance with the protocol and with the following:

- Consensus ethical principles derived from international guidelines including the Declaration of Helsinki and Council for International Organizations of Medical Sciences International Ethical Guidelines.
- Applicable ICH GCP Guidelines.
- Applicable laws and regulatory requirements.
- The protocol, protocol amendments, ICF, IB, and other relevant documents (eg, advertisements) must be submitted to an IRB by the investigator and reviewed and approved by the IRB before the study is initiated.
- Any amendments to the protocol will require IRB approval before implementation of changes made to the study design, except for changes necessary to eliminate an immediate hazard to study participants.
- The investigator will be responsible for the following:
 - Providing written summaries of the status of the study to the IRB annually or more frequently in accordance with the requirements, policies, and procedures established by the IRB
 - Notifying the IRB of SAEs or other significant safety findings as required by IRB procedures
 - Providing oversight of the conduct of the study at the site and adherence to requirements of 21 CFR, ICH guidelines, the IRB, European regulation 536/2014 for clinical studies (if applicable), and all other applicable local regulations

10.2.2. Study Monitoring

Before an investigational site can enter a participant into the study, a representative of the Sponsor or its representatives will visit the investigational study site, onsite or remotely, to do the following:

- Determine the adequacy of the facilities
- Discuss with the investigator(s) and other personnel their responsibilities with regard to protocol adherence, and the responsibilities of the Sponsor or its representatives.
This will be documented in a clinical study agreement between the Sponsor, the designated CRO, and the investigator.

According to ICH GCP guidelines, the Sponsor of the study is responsible for ensuring the proper conduct of the study with regard to protocol adherence and validity of data recorded on the eCRFs. The study monitor's duties are to aid the investigator and the Sponsor in the maintenance of complete, accurate, legible, well-organized, and easily retrievable data. The study monitor will advise the investigator of the regulatory necessity for study-related monitoring, audits, IRB review, and inspection by providing direct access to the source data/documents. In addition, the study monitor will explain to and interpret for the investigator all regulations applicable to the clinical evaluation of a vaccine as documented in ICH guidelines.

It is the study monitor's responsibility to inspect the eCRFs and source documentation throughout the study to protect the rights of the participants; to verify adherence to the protocol; to verify completeness, accuracy, and consistency of the data; and to confirm adherence of study conduct to any local regulations. Details will be outlined in the Clinical Monitoring Plan. During the study, a monitor from the Sponsor or a representative will have regular contacts with the investigational site, for the following:

- Provide information and support to the investigator(s).
- Confirm that facilities remain acceptable.
- Confirm that the investigational team is adhering to the protocol, that the data are being accurately recorded in the eCRFs, and that vaccine accountability checks are being performed.
- Perform source data verification. This includes a comparison of the data in the eCRFs with the participant's medical records at the hospital or practice, and other records relevant to the study. This will require direct access to all original records for each participant (eg, clinical charts or electronic medical record system).
- Record and report any protocol deviations not previously sent.
- Confirm that AEs and SAEs have been properly documented on eCRFs, that any SAEs have been forwarded to the SAE Hotline, and that those SAEs that met criteria for reporting have been forwarded to the IRB.

The monitor will be available between visits if the investigator(s) or other staff need information or advice. Visits may occur onsite or remotely depending on the site or state's visitation restrictions.

